8.1.2. Discontinuation of Inadvertently Enrolled Patients

If the sponsor or investigator identify a patient who did not meet enrollment criteria and was inadvertently enrolled, then the patient should be discontinued from study treatment unless there are extenuating circumstances that make it medically necessary for the patient to continue on

study treatment. If the investigator and the sponsor clinical research physician (CRP) agree it is medically appropriate to continue, the investigator must obtain documented approval from the sponsor CRP to allow the inadvertently enrolled patient to continue in the study with or without treatment with investigational product. Safety follow up is as outlined in Section 2 (Schedule of Activities), Section 9.2 (Adverse Events), and Section 9.4 (Safety) of the protocol.

8.2. Discontinuation from the Study

patient will be discontinued from the study in the following circumstances:

- enrollment in any other clinical study involving an investigational product or enrollment in any other type of medical research judged not to be scientifically or medically compatible with this study
- participation in the study needs to be stopped for medical, safety, regulatory, or other reasons consistent with applicable laws, regulations, and good clinical practice (GCP)
- investigator decision
 - the investigator decides that the patient should be discontinued from the study
 - if the patient, for any reason, requires treatment with another therapeutic agent that has been demonstrated to be effective for treatment of the study indication, discontinuation from the study occurs prior to introduction of the new agent
- patient decision
 - the patient or the patient's designee, for example, parents or legal guardian requests to be withdrawn from the study.

Patients discontinuing from the study prematurely for any reason should complete AE and other safety follow-up per Section 2 (Schedule of Activities), Section 9.2 (Adverse Events), and Section 9.4 (Safety) of this protocol.

8.3. Lost to Follow-Up

A patient will be considered lost to follow-up if he or she repeatedly fails to return for scheduled visits and is unable to be contacted by the study site. Site personnel are expected to make diligent attempts to contact patients who fail to return for a scheduled visit or were otherwise unable to be followed up by the site.

9. Study Assessments and Procedures

Section 2 lists the Schedule of Activities, with the study procedures and their timing (including tolerance limits for timing).

Appendix 2 lists the laboratory tests that will be performed for this study.

Unless otherwise stated in the subsections below, all samples collected for specified laboratory tests will be destroyed within 60 days of receipt of confirmed test results. Certain samples may be retained for a longer period, if necessary, to comply with applicable laws, regulations, or laboratory certification standards.

9.1. Efficacy Assessments

9.1.1. Primary Efficacy Assessment: Global Improvement Scores

Global improvement scores will be assessed in the 4 grades by comparing the psoriatic findings: (1) resolved, (2) improved, (3) unchanged, or (4) worsened. The global improvement score is assessed based on the comparison of the psoriatic findings, Static Physician Global Assessment (sPGA), Psoriasis Area and Severity Index (PASI) score, and other evaluations with those at the baseline.

9.1.2. Secondary Efficacy Assessments

The following secondary and exploratory efficacy measures will be assessed in this study:

- Psoriasis Area and Severity Index (PASI)
- Static Physician Global Assessment (sPGA)
- Scalp Psoriasis Severity Index (PSSI)
- Percentage of Body Surface Area (BSA)
- GPP Severity Index

9.1.2.1. Psoriasis Area and Severity Index

The PASI combines an assessment of the extent of body surface involvement in 4 anatomical regions (head, trunk, arms, and legs) and the severity of desquamation (scaling), erythema, and plaque induration/infiltration (thickness) in each region, yielding an overall score of 0 (no Ps) to 72 (the most severe disease) (Fredriksson and Pettersson 1978). The PASI has been the most frequently used endpoint and measure of Ps severity in clinical trials (EMEA 2004 [WWW]; Menter et al. 2008).

9.1.2.2. Static Physician Global Assessment

The sPGA is the physician's determination of the patient's Ps lesions overall at a given time point. The sPGA is recommended as an endpoint to use efficacy in the treatment of Ps (EMEA 2004 [WWW]). Overall lesions are categorized by descriptions for induration, erythema, and scaling. For analysis of responses, the patient's Ps is assessed as clear (0), minimal (1), mild (2), moderate (3), severe (4), or very severe (5).

9.1.2.3. Scalp Psoriasis Severity Index

If the patient has scalp Ps at baseline, the PSSI will be used. The PSSI is a composite score derived from the sum scores for erythema, induration, and desquamation multiplied by a score for the extent of the scalp area involved (range 0 to 72).

9.1.2.4. Percentage of Body Surface Area

The investigator will evaluate the percentage involvement of Ps on each patient's BSA on a continuous scale from 0% (no involvement) to 100% (full involvement), in which 1% corresponds to the size of the patient's hand (including the palm, fingers and thumb) (National Psoriasis Foundation 2009 [WWW]).

9.1.2.5. Generalized Pustular Psoriasis Severity Index

The GPP Severity Index will be evaluated only for patients with pustular Ps at screening and at baseline. This is a composite score derived from the sum of scores for assessment of dermal symptoms, systemic symptoms, and laboratory findings (range, 0 to 17).

- **Assessment of Dermal Symptoms**

Assessment of dermal symptoms, according to the Japanese Dermatological Association GPP revised criteria (2010) (Iwatsuki et al. 2010 [WWW]) will be evaluated only for patients with pustular Ps at screening and at baseline. Skin symptoms will be assessed by the score with the area of erythema (on a 0 to 3 scale), area of confluent pustules (on a 0 to 3 scale), and area of skin edema (on a 0 to 3 scale). The total score will be assessed (range, 0 to 9).

- **Systemic symptoms and laboratory findings**

Systemic symptoms and laboratory findings, according to the Japanese Dermatological Association GPP revised criteria (2010) (Iwatsuki et al. 2010 [WWW]) will be evaluated only for patients with pustular Ps at screening and at baseline. It will be assessed by the score with fever (on a 0 to 2 scale), WBC (on a 0 to -2 scale), C-reactive protein (on a 0 to 2 scale) and Albumin (on a 0 to 2 scale). The total score will be assessed (range, 0 to 8).

9.1.3. Appropriateness of Assessments

All of the clinical and safety assessments in this study are standard, widely used, and generally recognized as reliable, accurate, and relevant.

9.2. Adverse Events

investigator is responsible for monitoring the safety of patients who have entered this study and for alerting Lilly or its designee to any event that seems unusual, even if this event may be considered an unanticipated benefit to the patient. The investigator will record all relevant AE/SAE information in the CRF.

The investigator is responsible for the appropriate medical care of patients during the study.

The investigator must document his/her review of each laboratory safety report.

The investigator remains responsible for following, through an appropriate health care option, AEs that are serious or otherwise medically important, considered related to the investigational product or the study, or that caused the patient to discontinue the investigational product before completing the study. The patient should be followed until the event resolves, stabilizes with appropriate diagnostic evaluation, or is reasonably explained. The frequency of follow-up evaluations of the AE is left to the discretion of the investigator.

Lack of drug effect is not an AE in clinical studies, because the purpose of the clinical study is to establish treatment effect.

After the ICF is signed, study site personnel will record via electronic data entry the occurrence and nature of each patient's preexisting conditions, including clinically significant signs and symptoms of the disease under treatment in the study. In addition, site personnel will record any change in the condition(s) and any new conditions as AEs. The investigator should record his/her assessment of the potential relatedness of each AE to protocol procedure or investigational product, via electronic data entry.

The investigator will interpret and document whether or not an AE has a reasonable possibility of being related to study treatment, study device, or a study procedure, taking into account the disease, concomitant treatment or pathologies.

A "reasonable possibility" means that there is a cause and effect relationship between the investigational product, study device and/or study procedure and the AE.

The investigator answers yes/no when making this assessment.

Planned surgeries and nonsurgical interventions should not be reported as AEs unless the underlying medical condition has worsened during the course of the study.

If a patient's investigational product is discontinued as a result of an AE, study site personnel must report this to Lilly or its designee via electronic data entry, clarifying if possible, the circumstances leading to any dosage modifications, or discontinuations of treatment.

9.2.1. Serious Adverse Events

An SAE is any AE from this study that results in one of the following outcomes:

- death
- initial or prolonged inpatient hospitalization
- a life-threatening experience (that is, immediate risk of dying)
- persistent or significant disability/incapacity
- congenital anomaly/birth defect

- important medical events that may not be immediately life-threatening or result in death or hospitalization but may jeopardize the patient or may require intervention to prevent one of the other outcomes listed in the definition above. Examples of such medical events include allergic bronchospasm requiring intensive treatment in an emergency room or at home, blood dyscrasias or convulsions that do not result in inpatient hospitalization, or the development of drug dependency or drug abuse.
- when a condition related to the prefilled syringes necessitates medical or surgical intervention to preclude either permanent impairment of a body function or permanent damage to a body structure, the serious outcome of “required intervention” will be assigned.

All AEs occurring after signing the ICF are recorded in the electronic data entry and assessed for serious criteria. The SAE reporting to the sponsor begins after the patient has signed the ICF and has received investigational product. However, if an SAE occurs after signing the ICF, but prior to receiving investigational product, the SAE should be reported to the sponsor as per SAE reporting requirements and timelines (see Section 9.2) if it is considered reasonably possibly related to study procedure.

Study site personnel must alert Lilly or its designee of any SAE within 24 hours of investigator awareness of the event via a sponsor-approved method. If alerts are issued via telephone, they are to be immediately followed with official notification on study-specific SAE forms. This 24-hour notification requirement refers to the initial SAE information and all follow-up SAE information. Patients with a serious hepatic AE should have additional data collected using the electronic data entry.

Pregnancy (during maternal or paternal exposure to investigational product) does not meet the definition of an AE. However, to fulfill regulatory requirements any pregnancy should be reported following the SAE process to collect data on the outcome for both mother and fetus.

Investigators are not obligated to actively seek AEs or SAEs in patients once they have discontinued and/or completed the study (the patient disposition CRF has been completed). However, if the investigator learns of any SAE, including a death, at any time after a patient has been discharged from the study, and he/she considers the event reasonably possibly related to the study treatment or study participation, the investigator must promptly notify Lilly.

9.2.1.1. Suspected Unexpected Serious Adverse Reactions

Suspected unexpected serious adverse reactions (SUSARs) are serious events that are not listed in the IB and that the investigator identifies as related to investigational product or study procedure. United States 21 CFR 312.32 and European Union Clinical Trial Directive 2001/20/EC and the associated detailed guidances or national regulatory requirements in participating countries require the reporting of SUSARs. Lilly has procedures that will be followed for the identification, recording and expedited reporting of SUSARs that are consistent with global regulations and the associated detailed guidances.

9.2.2. Adverse Events of Special Interest

The following AEs of special interest (AESIs) will be used to determine the safety and tolerability of ixekizumab over the range of doses selected for this clinical study.

Adverse events of special interest for ixekizumab are:

- cytopenias (leukopenia, neutropenia, and thrombocytopenia)
- liver function test changes/enzyme elevations (ALT, AST, bilirubin, and alkaline phosphatase)
- infection
- injection-site reactions
- allergic reactions/hypersensitivities
- cerebrocardiovascular events
- malignancies
- inflammatory bowel disease
- depression
- interstitial lung disease (ILD).

If infections, injection-site reactions, or allergic/hypersensitivity reactions are reported, sites will provide details on these events as instructed on the CRF. Investigators will also educate patients and/or caregivers about the symptoms of allergic/hypersensitivity reactions and will provide instructions on dealing with these reactions. A blood sample will be collected when possible for any patient who experiences an AE of allergic/hypersensitivity reactions during the study.

Data on preferred terms associated with cerebrocardiovascular events (defined as death, cardiac ischemic events including MI and hospitalization for unstable angina, hospitalization for heart failure, serious arrhythmia, resuscitated sudden death, cardiogenic shock, coronary revascularization procedure, stroke/transient ischemic attack, peripheral revascularization procedure, and peripheral arterial event and hospitalization for hypertension) will be collected, and these events and any deaths will be adjudicated by an external Clinical Events Committee (CEC) made up of a chairman, 2 cardiologists, and a neurologist.

Data on suspected IBD, as identified by events possibly indicative of ulcerative colitis and Crohn's disease, will be collected and the events will be adjudicated by an external CEC with expertise in IBD.

The role of external CECs is to adjudicate defined clinical events in a blinded, consistent, and unbiased manner throughout the course of a study. The purpose of the CEC for adjudication of cerebrocardiovascular events and the CEC for adjudication of suspected IBD events is to ensure that all reported events are evaluated uniformly by a single group.

9.2.3. Complaint Handling

Lilly collects product complaints on investigational products and drug delivery systems used in clinical studies in order to ensure the safety of study participants, monitor quality, and to facilitate process and product improvements.

A patient will be instructed to contact the investigator as soon as possible if he or she has a complaint or problem with the investigational product or drug delivery system so that the situation can be assessed.

9.3. Treatment of Overdose

Refer to the Taltz IB and/or Product Label.

9.4. Safety

9.4.1. Electrocardiograms

For each patient, electrocardiograms (ECGs) should be collected locally according to the Schedule of Activities (Section 2). Patients are to be resting for 5 minutes prior to the ECG. It is recommended that patients be in a supine position. The qualified physician must document his/her review of the ECG at the time of screening.

The ECG results will be stored at the site and would be made available to the sponsor as requested. The investigators are allowed to repeat the ECG collection.

9.4.2. Vital Signs

For each patient, vital signs measurements should be conducted according to the Schedule of Activities (Section 2).

Vital signs (BP and pulse) and body temperature will be measured (sitting) after resting for a minimum of 10 minutes at times indicated in the Schedule of Activities (Section 2). At baseline (Week 0; Visit 2), BP and pulse should be measured prior to administration of the investigational product and again approximately 1 hour after administration. Any clinically significant findings from vital signs measurement that result in a diagnosis and that occur after the patient receives the first dose of study treatment should be reported to Lilly or its designee as an AE via CRF.

9.4.3. Laboratory Tests

For each patient, laboratory tests detailed in (Appendix 2) should be conducted according to the Schedule of Activities (Section 2).

Lilly or its designee will provide the investigator with the results of laboratory tests analyzed by a central vendor, if a central vendor is used for the clinical trial.

Any clinically significant findings from laboratory tests that result in a diagnosis and that occur after the patient receives the first dose of investigational product should be reported to Lilly or its designee as an AE via CRF.

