| 12-lead ECG ⁿ | X | | | | | | | | | | |
| FSH ^o | X | | | | | | | | | | |
| HIV/HBV/HCV ^p | X | | | | | | | | | | |
| HBV DNA ^q | X | | | X | X | X | | X | | X | X |
| Serum pregnancy test (Women of childbearing potential [WCBP] only) ^r | X | | | | | | | | | | |

| Procedure | Screening Period (Period 1) | Treatment Period - Induction (Period 2) | | | | | Treatment Period - Maintenance (Period 3) | | | | ETV |
|---|-----------------------------|---|---------|---------|---------|---------|---|----------|----------|----------|-----|
| | | V1 | V2 | V3 | V4 | V5 | V6 | V7 | V8 | V9 | |
| Visit Number | V1 | V2 | V3 | V4 | V5 | V6 | V7 | V8 | V9 | V10 | ETV |
| Study Week | - | 0 | 2 | 4 | 8 | 12 | 14 | 16 | 18 | 20 | |
| Visit Intervals | -30d to -7d | 0 | 14 ± 2d | 28 ± 4d | 56 ± 4d | 84 ± 2d | 98 ± 2d | 112 ± 2d | 126 ± 2d | 140 ± 2d | NA |
| Urine pregnancy test (WCBP only) ^r | | | | | | X | | | | X | X |
| Clinical chemistry | X | X | | | | X | | | | X | X |
| Hematology | X | X | | | | X | | | | X | X |
| Urinalysis | X | | | | | X | | | | X | X |
| hsCRP | | X | | | | X | | | | X | X |
| Beta-D-glucan ^s | X | | | | | | | | | | |
| KL-6 ^t | X | | | | | | | | | | |
| Immunogenicity testing ^u | | X | | | | X | | | | X | X |
| LY2439821 serum concentration ^{uv} | | | | | | X | | | | X | X |
| Pharmacogenetic sample (genetic sample/DNA) | X | | | | | | | | | | |

Abbreviations: AE = adverse event; AESI = adverse event of special interest; BP = blood pressure; BSA = body surface area; C-SSRS = Columbia- Suicide Severity Rating Scale; d = days; DLQI = Dermatology Life Quality Index; DNA = deoxyribonucleic acid; ECG = electrocardiogram; ETV = early termination visit; FSH = follicular stimulating hormone; GPP = generalized pustular psoriasis; HBcAb = hepatitis B core antibody; HBsAb = hepatitis B surface antibody; HBV = hepatitis B virus; HCV = hepatitis C virus; HIV = human immunodeficiency virus; hsCRP = high sensitivity C-reactive protein; IL-36 RN = interleukin 36 receptor antagonist; IP = investigational product; KL-6 = Kerbs von Lungren 6 antigen; NA = not applicable; NRS = numeric rating scale; PASI = Psoriasis Area and Severity Index; PCP = pneumocystis pneumonia; PPD = purified protein derivative; Ps = psoriasis; PSSI = Psoriasis Scalp Severity Index; SAE = serious adverse event; SC = subcutaneous; sPGA = static Physician's Global Assessment; TB = tuberculosis; V = study visit.

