8.1. Discontinuation from Study Treatment

8.1.1. *Permanent Discontinuation from Study Treatment*

Possible reasons leading to permanent discontinuation of investigational product:

- **Patient Decision**
 - the patient requests to discontinue investigational product.
- **Discontinuation due to a hepatic event or liver test abnormality.** A patient who is discontinued from investigational product due to a hepatic event or liver test abnormality should have additional hepatic safety data collected via CRF.

Discontinuation of the investigational product for abnormal liver tests **should be** considered by the investigator when a patient meets one of the following conditions after consultation with the Lilly designated medical monitor:

- ALT or AST >8X ULN
- ALT or AST >5X ULN for more than 2 weeks
- ALT or AST >3X ULN and total bilirubin level (TBL) >2X ULN or international normalized ratio (INR) >1.5
- ALT or AST >3X ULN with the appearance of fatigue, nausea, vomiting, right upper-quadrant pain or tenderness, fever, rash, and/or eosinophilia (>5%)
- alkaline phosphatase (ALP) >3X ULN
- ALP >2.5X ULN and TBL >2X ULN
- ALP >2.5X ULN with the appearance of fatigue, nausea, vomiting, right quadrant pain or tenderness, fever, rash, and/or eosinophilia (>5%)
- In addition, a patient who meets any one of the following criteria should be discontinued from the investigational product and conduct ETV, and discontinue from the study:
 - Absolute neutrophil (segmented) counts (see safety monitoring for neutropenia; Section 9.4.6.1):
 - <500 cells/ μ L
 - \geq 500 and <1000 cells/ μ L (based on 2 test results; the second test performed within 1 week from knowledge of the initial result).
 - \geq 1000 and <1500 cells/ μ L (based on 3 test results as specified in Section 9.4.6.1) - AND - an infection that is not fully resolved.
 - Total WBC count <2000 cells/ μ L (<2.00 x 10³/ μ L).
 - Lymphocyte count <500 cells/ μ L (<0.50 x 10³/ μ L).
 - Platelet count <50,000 cells/ μ L (<50 x 10³/ μ L).

- The patient experiences a severe AE, an SAE, or a clinically significant change in a laboratory value occurs that, in the opinion of the investigator, merits the discontinuation of the investigational product.
- Clinically significant systemic hypersensitivity event following administration of investigational product that does not respond to symptomatic medication or results in clinical sequelae.
- The patient becomes pregnant.

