9.4.6.2. Hepatic Safety Monitoring

If a study patient experiences elevated ALT $\geq 3X$ ULN, ALP $\geq 2X$ ULN, or elevated TBL $\geq 2X$ ULN, liver testing ([Appendix 4](#)) should be repeated within 3 to 5 days including ALT, AST, ALP, TBL, direct bilirubin, gamma-glutamyl transferase, and creatine kinase to confirm the abnormality and to determine if it is increasing or decreasing. If the abnormality persists or worsens, clinical and laboratory monitoring should be initiated by the investigator and in consultation with the study medical monitor. Monitoring of ALT, AST, TBL, and ALP should continue until levels normalize or return to approximate baseline levels.

Hepatic Safety Data Collection

Additional safety data should be collected via the electronic case report form (CRF) if 1 or more of the following conditions occur:

- elevation of serum ALT to $\geq 5X$ ULN on 2 or more consecutive blood tests
- elevated serum TBL to $\geq 2X$ ULN (except for cases of known Gilbert's syndrome)
- elevation of serum ALP to $\geq 2X$ ULN on 2 or more consecutive blood tests
- patient discontinued from treatment due to a hepatic event or abnormality of liver tests
- hepatic event considered to be a SAE

See Section [9.4.5.4](#) with regards to hepatitis B monitoring.

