Appendix 2. Clinical Laboratory Tests

Clinical Laboratory Tests^a

Hematology^b

Hemoglobin
 Hematocrit
 Erythrocyte count (RBC)
 Mean cell volume
 Mean cell hemoglobin concentration
 Leukocytes (WBC)
 Platelets
Absolute Counts of:
 Neutrophils, segmented
 Neutrophils, juvenile
 Lymphocytes
 Monocytes
 Eosinophils
 Basophils

Urinalysis (dipstick)^b

Color
 Specific Gravity
 pH
 Protein
 Glucose
 Ketones
 Bilirubin
 Urobilinogen
 Blood
 Nitrite
 Urine Creatinine
 Leukocyte esterase

Clinical Chemistry^b

Sodium
 Potassium
 Bicarbonate
 Chloride
 Phosphorus
 Total bilirubin
 Direct bilirubin
 Alanine aminotransferase (ALT/SGPT)
 Aspartate aminotransferase AST/SGOT)
 Blood urea nitrogen (BUN)
 Uric acid
 Creatinine
 Calcium
 Albumin
 Gamma-glutamyl transferase (GGT)
 Total protein

Other Tests

Human immunodeficiency virus antibody (HIV)
 Hepatitis B virus DNA^c
 Hepatitis B Surface antigen (HBsAg)
 Hepatitis B Core antibody (HBcAb)
 Hepatitis C antibody
 Hepatitis E antibody^d
 High Sensitivity C-reactive protein (CRP)
 Purified Protein Derivative (PPD)^e
 Pregnancy test (serum and urine)^f
 Follicle-stimulating hormone (FSH)^g

LY2439821 serum concentration^h

Immunogenicity testing (anti-ixekizumab Ab)^h

Beta-D-Glucanⁱ

KL-6ⁱ

Abbreviations: Ab = antibody; ALT = alanine aminotransferase; AST = aspartate aminotransferase; BUN = blood urea nitrogen; CRP = C-reactive protein; DNA = deoxyribonucleic acid; FSH = follicle stimulating hormone; GGT = gamma-glutamyl transferase; HbsAg = hepatitis B surface antigen; HBcAb = hepatitis B core antibody; HIV = human immunodeficiency virus; RBC = red blood cells; PPD = purified protein derivative; SGOT = serum glutamic-oxaloacetic transaminase; SGPT = serum glutamic-pyruvic transaminase; WBC = white blood cells.

- a Assayed by Lilly-designated laboratory.
- b Unscheduled or repeat blood chemistry, hematology, and urinalysis panels may be performed at the discretion of the investigator, as needed.
- c If patient is HBcAb+ and/or HBsAB+, HBV DNA needs to be confirmed negative at screening and at least once every month in Periods 2 and 3.
- d Hepatitis E antibody is not a part of routine screening for this study; however, it may be required during the study for hepatic follow-up.
- e See section 9.4.5.2: The QuantiFERON-TB Gold/T-SPOT.TB test may be used instead of the PPD TB test, and is performed locally.

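### Appendix 2 omits alkaline phosphatase from the scheduled chemistry panel, so the plan's ALP-only liver rules have no scheduled input unless the laboratory runs it anyway

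*Protocol*

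**What the plan says.** Protocol Section 9 defines the role of the appendix: "Appendix 2 lists the laboratory tests that will be performed for this study". Section 9.4.3 then ties that list to the visit calendar: "For each patient, laboratory tests detailed in (Appendix 2) should be conducted according to the Schedule of Activities (Section 2".

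The Schedule of Activities (Section 2) has one chemistry row, "Clinical chemistry | X | X | | | | X | | | | X | X", which marks V1, V2, V6, V10 and the early termination visit (ETV). It has no row for ALP.

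The text elsewhere uses ALP as a working safety measure:

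- Section 8.1.1 gives "alkaline phosphatase (ALP) >3X ULN" as a condition, sufficient alone, for considering discontinuation.
- Section 9.4.6.2 makes ALP at or above 2X ULN one of the triggers after which liver testing "should be repeated within 3 to 5 days including ALT, AST, ALP, TBL, direct bilirubin, gamma-glutamyl transferase, and creatine kinase".
- The same section requires extra CRF data for "elevation of serum ALP to" 2X ULN or more on successive tests, and sets the end of follow-up: "Monitoring of ALT, AST, TBL, and ALP should continue until levels normalize or return to approximate baseline levels".
- Section 9.2.2 names ALP in the liver adverse event of special interest.
- SAP Section 6.13.4.1 defines ALP abnormality categories, a listing criterion at 1.5X ULN, and a listing of ALP by visit.

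**The concern.** The rules on what to do about ALP presuppose a value that the list of scheduled tests does not supply. A retest after an ALP threshold is crossed needs an earlier ALP result. A return to roughly baseline needs a baseline. A by-visit listing needs values at visits.

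If the laboratory follows Appendix 2 literally, an isolated ALP rise without symptoms at Week 12 or at Week 20/ETV could go unseen. The absence of ALP abnormalities in the SAP listing could then be misread as normal ALP, when it would mean that ALP was not measured. The study is meant to describe the safety, as well as the efficacy, of Q2W dosing beyond Week 12, and liver enzyme changes including ALP are a named topic of interest.

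**Working it through.** **Is ALP scheduled anywhere?** The plan gives no figure to reproduce, so the check compares lists.

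1. The 16 analytes of the Appendix 2 chemistry panel are sodium, potassium, bicarbonate, chloride, phosphorus, total bilirubin, direct bilirubin, ALT, AST, urea nitrogen, uric acid, creatinine, calcium, albumin, GGT and total protein. ALP is absent. It is also absent under hematology, urinalysis and other tests.
2. Footnote b of Appendix 2 allows unscheduled or repeat panels, but these are the same panels and add no ALP.
3. ALP is measured in two places only. One is the Section 9.4.6.2 repeat panel, which starts after ALT, ALP or total bilirubin (TBL) crosses its threshold. The other is Appendix 4, which is optional and needs a hepatic abnormality to have emerged. GGT is scheduled but is not a Section 9.4.6.2 trigger.

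Scheduled ALP measurements as written: 0, including 0 before the first dose.

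**Which rules depend on a stand-alone ALP value?**

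| Location | Items | Needing ALP alone |
|---|---|---|
| Protocol 8.1.1, liver conditions | 4 on ALT/AST + 3 on ALP = 7 | 1 |
| Protocol 9.4.6.2, retest triggers | ALT, ALP, TBL = 3 | 1 |
| Protocol 9.4.6.2, CRF conditions | ALT, TBL, ALP, discontinuation, SAE = 5 | 1 |
| SAP 6.13.4.1, category sets | ALT/AST, TBL, ALP = 3 | 1 |
| SAP 6.13.4.1, listing criteria | ALT with TBL, ALT/AST, TBL, ALP = 4 | 1 |

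In Section 8.1.1, the condition pairing ALP with bilirubin can be reached through routine bilirubin and the repeat panel. The condition pairing ALP with symptoms can be reached through clinical presentation and Appendix 4. Only ALP above 3X ULN alone has no route.

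**How many samples would lack ALP if the laboratory does not run it?** Assume 12 enrolled, no dropout, and the V2 sample taken before dosing. Let k be the number entering Period 3, each contributing one further sample at V10 or ETV.

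- Total = 12 × 3 (V1, V2, V6) + k = 36 + k
- Pre-dose = 12 × 2 = 24
- Post-dose = 12 (V6) + k
- Samples that could bear on dosing = k (the V6 sample in patients who continue)

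| k | Total | Pre-dose | Post-dose | Could bear on dosing |
|---|---|---|---|---|
| 5 (the maximum of about 5 mentioned in Protocol 10.1) | 41 | 24 | 17 | 5 |
| 10 (5 EP + 5 GPP, the design target) | 46 | 24 | 22 | 10 |
| 12 (all enrolled) | 48 | 24 | 24 | 12 |

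After the Week 12 dose, three doses remain (Weeks 14, 16 and 18).

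These are counts of samples, not of missed events. The documents give no rate for isolated ALP rises.

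**The case against.** The strongest reply is that Appendix 2 is not exhaustive. It also lists neither HBsAb nor HCV RNA, although both are needed at screening. Read together, the ALP retest trigger, the discontinuation threshold, the special-interest definition and the by-visit listing suggest that routine ALP was intended. The laboratory may well run it. A line lost in reading the PDF also cannot be excluded. On this view there is a slip in a list and no gap in monitoring.

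Much of this stands as a statement of likely intent, and the conclusion is conditional for that reason. The comparison with the hepatitis tests is imperfect, however. Other sections explicitly require those results at screening, whereas no section orders a routine ALP. The extracted chemistry list also reads as continuous.

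Three further points limit the consequences, and all hold:

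- Normalization alone ends follow-up under Section 9.4.6.2, so a missing baseline matters mainly for a patient whose ALP was already raised before treatment.
- Scheduled ALT, AST, GGT and bilirubin remain, and an ALT or bilirubin trigger brings ALP in.
- SAP Section 6.13.4 lists all laboratory values, so a reader could see whether ALP was measured. SAP Version 2 was approved before the final analysis, so a change to Appendix 2 may come too late to add data.

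**Conclusion.** The point holds. As written, the plan schedules no ALP measurement while several of its rules need one. The gap is narrow: the isolated, asymptomatic ALP rise, and the absence of a pre-treatment value.

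Its size turns on the central-laboratory panel, which the documents do not show. With ALP on that panel, no value is lost and this is a one-line list error. Without it, every scheduled chemistry sample counted above lacks ALP, and only the Week 12 values in continuing patients could influence dosing. Even there, Section 8.1.1 asks for consideration with the medical monitor and does not impose an automatic stop. Reporting harm is small, although the SAP's ALP categories and by-visit ALP would be largely unfilled. No efficacy result is touched.

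Confidence is medium, because of the unseen laboratory specification and the possibility of an extraction loss. The correction is still worthwhile because it costs almost nothing and supports a liver signal on which the plan relies.

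**What to change.** Add alkaline phosphatase to the clinical chemistry panel in Appendix 2 and confirm it in the central-laboratory specification, run on blood already drawn at V1, V2, V6 and V10/ETV. No threshold changes. If the laboratory already reports ALP, only the list needs correcting.

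If samples have been processed without routine ALP, add one sentence beside the SAP Section 6.13.4.1 ALP listing saying so.

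HBsAb and HCV RNA can be added to the other-tests list at the same time. That is clerical, since other sections already require them.

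The cost is one line in the appendix and one check of the specification, or one sentence in the report.
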